7.4 Exploratory Analyses

Analysis of the following exploratory endpoints may be undertaken as deemed appropriate.

Exploratory Efficacy Endpoint	Variable Derivation [Source]	Summary Statistics [Analysis Set]	Method of Analysis
Mean change in SD-OCT central subfield thickness (CST) from baseline until switch to Schedule B by visit over time	Continuous Endpoint: Change from baseline to each time point	Mean/Median [Patients who switch to Schedule B], until switch to Schedule B	Descriptive
Mean change in BCVA from baseline until switch to Schedule B by visit over time	Continuous Endpoint: Change from baseline to each time point [Visual Acuity Score/EDC]	Mean/Median [Patients who switch to Schedule B], until switch to Schedule B	Descriptive
Mean change in SD-OCT central subfield thickness (CST) from time moved to Schedule B until end of follow- up by visit over time	Continuous Endpoint: Change from time moved to Schedule B to each time point [EDC]	Mean/Median [Patients who switch to Schedule B], until end of follow-up	Descriptive
Mean change in BCVA from time moved to Schedule B until end of follow-up by visit over time	Continuous Endpoint: Change from time moved to Schedule B to each time point [Visual Acuity Score/EDC]	Mean/Median [Patients who switch to Schedule B], until end of follow-up	Descriptive

Table 5: Exploratory Efficacy Endpoints and Analysis Methods

7.5 Subgroup Analyses

For each of the subgroups listed in Table 2, the primary efficacy endpoint (i.e., proportion of eyes improving ≥ 2 steps on DRSS from baseline at Week 48) will be analyzed using the CMH method described in Section 7.1.2. When a subgroup is a part of the randomization stratification variable, the corresponding stratification variable will be removed from the stratified CMH test.

A forest plot will be provided to present the treatment effect of these subgroups.

8.0 SAFETY EVALUATION

Safety analyses will be performed for the Safety Analysis Set. In the Primary Analysis, safety data from Day 1 to Week 48 will be summarized by treatment group.

8.1 Exposure to Study Medication

Study eye exposure to study medication will be summarized (open-label KSI-301 5mg treatment will not be included here). Summaries will include:

- Mean (SD) and median number of injections, and number of patients receiving ≥1 injection, 1, 2, 3, 4, 5, etc. of KSI-301 or sham injections from Day 1 to Week 48 and from Day 1 to the end of study.
- Duration of study drug exposure (mean [SD] and median, in months) for subjects receiving KSI-301 5 mg or sham.
- Listings will include treatment (KSI-301, sham) and date of injection.

For patients who develop sight-threatening complication(s), exposure to open-label KSI-301 5mg treatment will be summarized and listed similarly as above.

A listing of patients who received study treatment other than the one assigned at randomization will include the randomized treatment, the actual administered treatment, Visit, and study Day. A separate listing will list patients who receive open-label KSI-301 5mg treatment with the same variables.

8.2 Adverse Events

Adverse events (AEs) will be coded to a MedDRA version 23.1 or later. AEs and Serious AEs (SAEs) will be summarized and listed by ocular events for the treated eye (or study eye), ocular events for the non-treated eye (or fellow eye), and non-ocular (systemic) events.

Treatment emergent AEs (TEAEs) are events with onset date on or after the initiation of study treatment through the last dose date of study treatment + 28 days, start date of non-study anti-

VEGF in study eye on or after last dose date, or start date of open-label KSI-301 treatment due to development of sight-threatening complication, whichever occurs first.

If the severity score of an adverse event is missing, the severity score will be imputed as severe. If the relatedness of an adverse event is missing, the adverse event will be considered related.

At each level of summarization (e.g., any AE, system organ class, and preferred term), subjects experiencing more than one TEAE will be counted only once. In the summary of TEAEs by severity grade, subjects will be counted once at the highest severity reported at each level of summarization.

Frequency tables including patients' incidence rates will be provided through Week 48 for the following:

- Ocular TEAEs and treatment-emergent serious AEs (TESAEs) (study eye and fellow eye separately)
- Non-ocular TEAEs and TESAEs
- Ocular TEAEs leading to study treatment discontinuation (study eye and fellow eye separately)
- Ocular TEAEs by severity (study eye and fellow eye separately)
- Non-ocular TEAEs by severity
- Related ocular TEAEs (study eye and fellow eye separately) by severity
- Related non-ocular TEAEs by severity
- Intraocular inflammation TEAEs and TESAEs not associated with infection, autoimmunity, drug toxicity, or traumatic etiologies (study and fellow eye separately).
- IOI TEAEs and TESAEs associated with infection (study and fellow eye separately).
- IOI TEAEs and TESAEs associated with autoimmune, drug toxicity, or trauma (study and fellow eye separately).
- Arteriothromboembolic (ATE) Adverse Events. ATEs will be tabulated as those events meeting the Anti-Platelet Trialists' Collaboration criteria (i.e., nonfatal

myocardial infarction, nonfatal stroke, and vascular death, including deaths of unknown cause)

- Adverse events of special interest [AESI] (study eye, fellow eye and non-ocular combined), as defined in the protocol Section 8.3.6
- Injection procedure related TEAEs and TESAEs in study eye
- Non-serious TEAEs and TESAEs (study eye, fellow eye and non-ocular combined)

All AEs and serious AEs will be presented separately in data listings by treatment group, subject ID, and event date. Adverse events from patients who remain in the study after study treatment discontinuation will be listed.

For subjects who receive open-label KSI-301 5mg treatment due to development of sightthreatening complications, ocular TEAEs and TESAEs for study eye starting from when subjects switch to open-label KSI-301 treatment will be summarized until the end of study. All AEs (study eye, fellow eye and non-ocular) will be presented in a data listing by subject ID, and event date.

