8.3 Adverse Events, Serious Adverse Events, and Other Safety Reporting

The definitions of AEs and SAEs are provided in Appendix 3.

AEs will be reported by the participant (or, when appropriate, by a caregiver, surrogate, or the participant's legally authorized representative).

The Investigator and any qualified designees are responsible for detecting, documenting, and recording events that meet the definition of an AE or SAE and remain responsible for following up AEs that are serious, considered related to the study intervention or study procedures, or that caused the participant to discontinue the study (Section 7.0).

The method of recording, evaluating, and assessing causality of AEs and SAEs and the procedures for completing and transmitting SAE reports are provided in Appendix 3.

8.3.1 Time Period and Frequency for Collecting Adverse Event and Serious Adverse Event Information

After informed consent has been obtained but prior to initiation of study intervention, only SAEs caused by a protocol-mandated assessment should be reported. After initiation of study intervention (Day 1), all AE and SAE information will be collected until the final safety follow-up visit at Week 100 or the ET visit, if applicable.

All SAEs will be recorded and reported to the Sponsor or designee immediately and under no circumstance should this exceed 24 hours, as indicated in Appendix 3. The Investigator will submit any updated SAE data to the Sponsor within 24 hours of it being available.

Investigators are not obligated to actively seek information on AEs or SAEs after conclusion of the study participation. However, if the Investigator learns of any SAE, including a death, at any time after a participant has been discharged from the study, and he/she considers the event to be reasonably related to the study intervention or study participation, the Investigator must promptly notify the Sponsor.

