5.2 Standard Calculations

Where appropriate, the calculated study day will be presented with the assessment or event date on subject data listings. Study day will be determined as:

- The assessment/event date minus the date of first dose of study drug, if the assessment/event date is prior to the date of first dose; and
- The assessment/event date minus the date of first dose of study drug, plus one, if the assessment/event date is on or after the date of first dose.

Start and stop dates will be imputed when partial dates are present as needed, to determine treatment emergent events and concomitant medications/procedures. No imputations will be done for a completely missing start/stop date or for subjects who did not receive study treatment.

Start dates with a missing day but with month and year available will be imputed such that:

- If the provided month and year match the month and year for that subject's first dose date, then the Day 1 date will be used.
- In all other cases the 1st of the month will be used with the provided month and year.

Start dates with a missing day and month but with available year will be imputed such that:

- If the provided year matches the year for that subject's first dose date, then the first dose date will be used.
- In all other cases the 1st of January will be used with the provided year.

Stop dates will be imputed as follows:

- Missing day with a provided year and month will use the last day of the month.
- Missing day and month with provided year will use December 31.

If the imputed stop date is greater than the last study date for the subject, then the imputed date will be replaced with the last available event date for the subject in the study.

Other variables requiring calculations will be derived using the following formulas:

- Days: A duration between two dates expressed in days will be calculated using the following conventions:
 - Later date earlier date + 1.
- Months: A duration expressed in months will be calculated by dividing the duration in days by (365.25 /12).
- Years: A duration expressed in years will be calculated by dividing the duration in days by 365.25.

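### The SAP's adverse-event date rules give no default for an undated event and ignore the open-label switch date, so a few events can be left out of the TEAE tables or counted in the wrong one

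*SAP*

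**What the plan says.** **Window.** SAP 8.2 opens the treatment-emergent window at first treatment ("Treatment emergent AEs (TEAEs) are events with onset date on or after the initiation of study treatment"). It closes the window at the earliest of three dates. Two matter here: "through the last dose date of study treatment + 28 days" and "start date of open-label KSI-301 treatment due to development of sight-threatening complication, whichever occurs first". The third is the start of non-study anti-VEGF in the study eye.

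**Open-label table.** For participants who switch, study-eye ocular events "starting from when subjects switch to open-label KSI-301 treatment will be summarized until the end of study". Fellow-eye and non-ocular events after the switch are listed but not tabulated there.

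**Dates.** SAP 5.2 imputes partial dates in order to decide treatment emergence, but "No imputations will be done for a completely missing start/stop date or for subjects who did not receive study treatment". If only the day is missing and the month is the first-dose month, the Day 1 date is used. For other months, "In all other cases the 1st of the month will be used with the provided month and year". If only the year is known, the first dose date is used when the year matches, and otherwise 1 January.

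**Other missing items.** SAP 8.2 says "If the severity score of an adverse event is missing, the severity score will be imputed as severe" and treats missing relatedness as related.

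**Collection.** Under Protocol 8.3.1, before first treatment "only SAEs caused by a protocol-mandated assessment should be reported". From Day 1 all adverse events are collected, to Week 100 or early termination.

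**The concern.** There are two gaps.

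1. An event with no onset date cannot be shown to satisfy a definition that rests on onset date, and the SAP does not say how to classify it. Severity and relatedness default to the cautious side. A completely missing onset date has no default.

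2. The open-label start is a second boundary. It closes the masked window and opens the open-label table, but the partial-date rules never refer to it. Moving a date to the start of its month or year can carry an event from after a sham participant's first real injection to before it.

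At stake are the descriptive safety tables, above all study-eye events soon after a sham participant first receives KSI-301. Where counts are low, one or two misplaced records can change how a row reads.

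**Working it through.** The documents state no figure on this point, so there is none to reproduce. The check applies the SAP 5.2 and 8.2 rules as written.

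**Undated event.** The definition needs onset on or after first treatment. Onset is unknown and is not imputed, so the condition cannot be evaluated. On a strict reading the event is in no TEAE table. This is an inference from the SAP's silence, not something the SAP states.

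**Worked example, partial date.** Assume first dose on 10 January 2022 and a switch at Week 32.
- Switch: 10 January + 224 days = 22 August.
- Last masked dose, Week 20: 10 January + 140 days = 30 May.
- Masked window closes 28 days later: 27 June.

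| True onset | Known part | Imputed | Where it is counted |
|---|---|---|---|
| 27 August | month, year | 1 August | neither table (after 27 June, before 22 August) |
| 27 August | year | 10 January | masked-period table |
| 1 October | month, year | 1 October | open-label table (correct) |
| 1 October | year | 10 January | masked-period table |

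**How often, given an incomplete date.** The rules were applied to every onset day from switch to Week 100, for switches at Weeks 8, 20, 32, 44 and 48, over 365 first-dose dates from September 2021. Assumptions: onset spread evenly, visits on schedule, and the last dose date in SAP 8.2 read as the last masked dose.

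| Switch | Day missing: leave open-label table | Of these: masked / neither | Year only: leave open-label table | Of these: masked / neither |
|---|---|---|---|---|
| Week 8 | 2.3% | 1% / 99% | 28.3% | 86% / 14% |
| Week 20 | 2.6% | 0% / 100% | 32.5% | 72% / 28% |
| Week 32 | 3.1% | 0% / 100% | 38.2% | 72% / 28% |
| Week 44 | 3.8% | 0% / 100% | 46.4% | 38% / 62% |
| Week 48 | 4.0% | 100% / 0% | 50.0% | 100% / 0% |

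Every event that leaves has its true onset in the switch's calendar month (day missing) or calendar year (year only). Within that month 93.6% leave; within that year 99.5% leave. The first figure can be checked by hand. In a 30-day month with the switch equally likely on any day, there are 30 + 29 + … + 1 = 465 pairs of switch day and onset day. Only the 30 pairs with a switch on the 1st stay, so 435/465 = 93.5% leave.

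**Soon after the switch.** Take onset 1 to 28 days after the switch and the same 30-day month. Of 30 × 28 = 840 pairs, 434 (52%) have onset in the switch month. Removing the 28 pairs with a switch on the 1st leaves 406/840 = 48% that would be dated before the switch if the day were missing. The exposure is concentrated in the first weeks of open-label treatment.

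**Why neither table is common.** At Weeks 8, 20, 32 and 44 the previous masked dose was 8, 12, 12 and 24 weeks earlier, so the 28-day window closed at least 4 weeks before the switch. At Week 48 the last masked dose was 4 weeks earlier and the window reaches the switch itself.

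**The case against.** The strongest reply is that this concerns a few records in descriptive tables. All adverse events are listed (SAP 8.2). Deaths, serious events and events leading to interruption or withdrawal have further listings (SAP 8.3). The arterial thromboembolic and special-interest tables are not worded as TEAE-only. Serious and special-interest events are reported within 24 hours, and data are cleaned before the freeze, so nothing suggests that those events in particular would lack a month. This stands, and it limits the size of the problem. It does not close either gap, because a listing does not correct an incidence table.

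A reader might also infer more than the documents support:

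- *Every partly dated post-switch event leaves the open-label table.* It does not. With the day missing, events in later months stay. Partial dates matching the first-dose month or year go to first dose, which keeps the event treatment-emergent.
- *An undated event must be treatment-emergent, because collection starts at Day 1.* That settles only the lower bound. The window also has an upper bound, and collection runs to Week 100. Protocol 10.3.1 also counts conditions first detected after dosing that may have existed earlier.
- *The errors all favour KSI-301.* Some moved events are added to a TEAE table. For participants randomized to KSI-301, an event moved into the masked-period table is still attributed to KSI-301. Early imputation can also pull an event from after the window into it.
- *Events vanish from reporting.* They remain in the listings.

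**Conclusion.** The point holds in this limited form. The SAP has no rule for an undated adverse event, and its partial-date rule misclassifies certain study-eye events near the open-label switch. This is more than missing detail: followed as written, the rule puts the 27 August event in the example in no TEAE table.

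The size is conditional. Among post-switch onset days to Week 100, about 2–4% are exposed if the day is missing and about 28–50% if only the year is known. These shares rest on even onset, on-schedule visits and follow-up to Week 100. SAP 3.1 says data after Week 48 will be incomplete, and shorter follow-up would raise the day-missing share. The split between masked table and neither depends on reading the last dose as the last masked dose. If open-label doses count as study treatment, the masked window runs to the switch and the moved events fall in the masked-period table instead.

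The documents do not say how many dates are incomplete. The number of affected records is probably small, and no efficacy result is touched. The change is worth making because it is cheap and is better settled before unmasking than record by record afterwards.

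**What to change.** Add two rules to SAP 5.2 and 8.2.

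(a) Treat an adverse event with a completely missing onset date as treatment-emergent unless its stop date is before first dose. For a study-eye event in a participant who switched, assign it to one period only: open-label, unless the stop date or other recorded data place onset before the switch.

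(b) For study-eye ocular events in participants who switched, also compare the known date parts with the first open-label dose date. If the known parts, the stop date and other recorded data do not rule out onset on or after that dose, impute the switch date and count the event once, in the open-label table. State that for these events the masked window ends the day before the switch, so that none is counted twice.

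Keep the current SAP 5.2 rule for partly dated fellow-eye and non-ocular events. The open-label summary covers only study-eye ocular events, so moving the others to the switch date could leave them in no table.

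The cost is a few sentences and a small change to the date derivation. The downside is that some pre-switch study-eye events, mainly those with only the year known, may be attributed to open-label KSI-301. A footnote giving the number of events placed by these rules would let the reader judge that.

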4.1.3 Administration of Study Intervention

All participants will be treated starting on Day 1 through Week 92 according to their respective treatment group. The IRT will determine the dosing schedule and adjust it in consideration of missed visits, out of window visits, and missing data during a visit. If a visit is missed at which study treatment is scheduled to be administered, the missed dose should be made up as close to the originally scheduled visit as possible using an unscheduled visit. Adjustments to study intervention due to development of sight-threatening complications of DR are described in Section 4.1.3.1.

As shown in the dosing regimen schematic provided in Figure 1, participants will be treated according to the group to which they were randomized, as follows:

• Group A - KSI-301 5 mg via Intravitreal Injection:

Intravitreal KSI-301 5 mg injection will be administered on Day 1, Week 8, Week 20, Week 44, Week 68, and Week 92.

• Group B - Sham Injection:

To preserve study masking, sham injections are administered to Group B participants at visits in which KSI-301 is administered to Group A participants. Thus, sham injections will be administered on Day 1, Week 8, Week 20, Week 44, Week 68, and Week 92.

For all study participants, non-treatment study visits will occur on Week 32, Week 48, Week 56, Week 80, and Week 96. A final safety assessment will occur on Week 100 and will be done via telephone call for all participants, except in WOCBP, in which case a site visit is required to administer a pregnancy test.

		Year 1								PE				
Week		0	(4)	8	(12)	(16)	20	(24)	(28)	32	(36)	(40)	44	48
KSI-301 5 mg	Q24W													
Sham		0		0			0						0	
						Ĩ	Year 2						SE	SA
Week		(52)	56	(60)	(64)	68	(72)	(76)	80	(84)	(88)	92	96	100 ª
KSI-301 5 mg	Q24W													
Sham						0						0		

Figure 1: Protocol KS301P106: Masked Dosing Regimens by Week

Abbreviations: PE = primary endpoint; Q24W = once every 24 weeks; SA = safety assessment; SE = secondary endpoint.

^a Week 100 is a final safety assessment that will be done via telephone call for all participants, except in WOCBP, in which case a site visit is required for the safety assessment that includes a pregnancy test.

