Participants who develop any of the sight-threatening complications of DR in the Study Eye that are described in Table 3 will be treated with open-label KSI-301 5 mg, irrespective of the treatment group that they were originally randomized into (KSI-301 5 mg or sham). The original treatment group randomization will remain masked throughout the study.

At the visit that a sight-threatening complication of DR (DME, PDR and/or ASNV) is diagnosed (i.e., the "Dx Visit"), treatment with open-label KSI-301 5 mg will be initiated. Starting at the Dx Visit, participants will no longer follow the study visits and assessments outlined in Section 1.3.1 (SoA-A), nor receive further masked treatments. Instead, they will follow the study visits and assessments outlined in Section 1.3.2 (SoA-B), which is specific to the participants who develop DME, PDR, and/or ASNV.

As shown in Figure 2, treatment of DME, PDR, and/or ASNV will consist of the following:

 Two doses of KSI-301 5 mg, given four weeks apart (+/- 7 days), followed by KSI-301 5 mg once every 12 weeks (Q12W; +/-14 days). Thus, the first dose shall occur during the study visit in which DME, PDR, and/or ASNV was diagnosed, and the second dose shall occur 4 weeks (+/- 7 days) later. Thereafter, subsequent doses shall occur Q12W (+/-14 days).

More frequent visits and more frequent treatments with KSI-301 5 mg and/or panretinal photocoagulation (PRP) are at the discretion of the Investigator if the sight-threatening complication(s) as described in Table 3 are still present. Treatment with KSI-301 5 mg may not be given more often than monthly $(28 \pm 7 \text{ days})$.

End of Study Considerations

For participants who develop any of the sight-threatening complications described in Table 3, the following shall be considered:

- Participants shall not receive any treatment with KSI-301 5 mg after Week 92 (i.e., 92 weeks after the day of randomization (Day 1)).
- Weeks 96 and 100 (relative to the day of randomization (Day 1)) include final safety assessments that are mandatory and shall also be conducted according to the SoA-B (Section 1.3.2).

Figure 2:Protocol KS301P106: Dosing Regimen by Week for All Participants
Who Develop Sight-threatening Complication(s) in the Study Eye

	Q4W (±	7 days)	C	12W (± 14 day	SE	SA	
Week	Dx Visit	Dx Visit + 4 Weeks	Dx Visit + 16 Weeks	Dx Visit + 28 Weeks		96	100 ^b
KSI-301 5 mg ^a							
KSI-301 5 mg via intravitreal injection							treatment Visit

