7.0 DISCONTINUATION OF STUDY INTERVENTION AND PARTICIPANT DISCONTINUATION/WITHDRAWAL

7.1 Discontinuation of Study Intervention

Participants may withdraw from the study at any time and for any reason without prejudice to their future medical care by the Investigator or at the study site. Every effort should be made to keep participants in the study.

If study treatment is discontinued, an end-of-treatment visit should occur 28 +/- 7 days after study treatment is discontinued or before a new treatment regimen begins. Participants who discontinue study drug should NOT be considered withdrawn from the study. Unless they withdraw consent or there is additional risk to the participant, participants who have discontinued study treatment should be encouraged to stay in the study and undergo as many scheduled visits as possible, with emphasis on the Week 48 (primary endpoint) and Week 96 (secondary endpoint) visits.

The reasons for study treatment discontinuation and/or withdrawal from the study (study discontinuation) will be recorded on the appropriate eCRF.

A participant may be withdrawn from the study for any of the following reasons:

- 1. The participant is non-compliant with the protocol;
- 2. The participant has a serious or intolerable adverse event(s) (AE[s]) that in the Investigator's opinion requires withdrawal from the study;
- 3. The participant has symptoms or an intercurrent illness not consistent with the protocol requirements or that justify withdrawal;
- 4. The participant is lost to follow-up;
- 5. Any medical condition that the Investigator or Sponsor determines may jeopardize the participants' safety if they remain in the study;
- 6. The participant withdraws consent, or the Investigator or Sponsor decides to discontinue the participant's participation in the study; or
- 7. Pregnancy.

The Investigator will also withdraw a participant if the Sponsor terminates the study. Upon occurrence of a serious or intolerable AE, the Investigator will confer with the Sponsor. If a participant is discontinued because of an AE, the event will be followed until it is resolved, or no additional improvement is expected by the Investigator (based on a follow-up period of not less than 3 months). Any participant may withdraw his or her consent at any time.

7.1.1 Treatment Interruption and/or Discontinuation due to Adverse Events or Concomitant Procedures

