Study treatment interruption and/or participant discontinuation from the study treatment due to certain adverse events or concomitant procedures in the Study Eye will be determined using the criteria provided in Table 5. If any of these are met, treatment will be interrupted (or discontinued if applicable) and notification will be sent to the medical monitor. Treatment may be resumed after resolution of the adverse event and upon agreement with both the Investigator and medical monitor. The reason for study treatment interruption or discontinuation should be recorded on the appropriate eCRF and, if applicable, on the Adverse Event eCRF.

Event (MedDRA Preferred Term)	Study Treatment Interruption Criteria	
Vision loss	Interrupt study treatment for treatment-related decrease of \geq 30 letters in BCVA in the Study Eye compared with the most recent prior visit.	
Intraocular inflammation	Interrupt study treatment if any active intraocular inflammation is present in the Study Eye.	
Intraocular surgery	Interrupt study treatment for intraocular surgery in the Study Eye, for example cataract surgery.	
	Treatment may resume no earlier than 10 days after uncomplicated cataract surgery, provided there is no evidence of post-operative intraocular inflammation. For complicated cataract surgery or following other intraocular surgery, study treatment may be resumed as determined by the	
	Investigator following discussion with the Medical Monitor.	
Elevated intraocular pressure	Interrupt study treatment if the pre-injection IOP is >30 mmHg in the Study Eye.	
Retinal tear or break	Interrupt study treatment if a retinal tear or break is present in the Study Eye.	
	Treatment may be resumed no earlier than 10 days after successful laser retinopexy, as determined by the Investigator.	
Retinal detachment or macular hole	Interrupt study treatment if rhegmatogenous retinal detachment or Stage 3 or Stage 4 macular hole occurs in the Study Eye.	
	Treatment may be resumed no earlier than 14 days after successful treatment, as determined by the Investigator, following discussion with the Medical Monitor.	
Active infection	Interrupt study treatment if infectious cellulitis, conjunctivitis, keratitis, scleritis, or endophthalmitis occurs in or around either eye. Infections should be treated as per the local standard of care.	

Table 5: Protocol KS301P106: Treatment Interruption Criteria

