9.4.5 Safety Analysis

The safety analysis (using the safety population described in Section 9.3) will use outcomes of all participants who were exposed to study treatment regardless of adherence to the protocol or treatment outcome. Safety analyses will be conducted concurrently with efficacy analyses.

In addition to analyses of ocular safety events, all reported adverse events will be listed by MedDRA term, frequency, severity, association to the study therapy, and treatment group. By-treatment incidence rates will also be calculated for the treatment groups. For certain adverse events, per-injection rates will also be described.

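### The AE tables named in SAP 8.2 stop counting 28 days after the last dose, so late events in participants who stop masked treatment but stay in the study are missed

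*SAP*

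**What the plan says.** SAP 8.2 counts as treatment-emergent the "events with onset date on or after the initiation of study treatment through the last dose date of study treatment + 28 days". The window closes earlier if non-study anti-VEGF is given in the study eye or open-label KSI-301 is started. Apart from the ATE and AESI tables, every frequency table named there is worded as TEAE or TESAE. The only discontinuation table covers ocular TEAEs. AEs in participants who stay in the study after stopping treatment go to a listing.

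Other parts of the plan set a wider scope:
- SAP Table 1 gives the safety endpoint as the incidence of ocular and systemic AEs up to Week 48, with no treatment-emergent restriction.
- SAP 8.0 says "safety data from Day 1 to Week 48 will be summarized by treatment group".
- Protocol 9.4.5 says the safety analysis "will use outcomes of all participants who were exposed to study treatment regardless of adherence to the protocol or treatment outcome", and adds: "By-treatment incidence rates will also be calculated for the treatment groups".
- The opening of SAP 8.2 says AEs and SAEs will be both summarised and listed, but the list of tables that follows names no all-AE or all-SAE table.

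On dosing, Protocol 4.1.3 states: "Intravitreal KSI-301 5 mg injection will be administered on Day 1, Week 8, Week 20, Week 44, Week 68, and Week 92". Sham follows the same schedule. Protocol 7.1 says "participants who have discontinued study treatment should be encouraged to stay in the study and undergo as many scheduled visits as possible".

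**The concern.** A 28-day tail is short beside dosing intervals of 8, 12 and 24 weeks. While dosing continues this does no harm, because the window runs unbroken from first to last dose. Once dosing stops for good, the window closes 28 days after a dose that may lie months before the decision to stop.

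Take a participant last dosed at Week 20 who has non-severe intraocular inflammation at Week 30 and is never dosed again. The window closed at Week 24. The event is in neither the inflammation table nor the discontinuation table, although SAP 6.1 counts the reason for stopping. For such participants the reported Week 48 incidence of AEs, SAEs, inflammation and AE-related discontinuation can be too low, and the discontinuation table can disagree with disposition. SAP 10.0 cancels the Week 100 analyses, so no later planned analysis would recover these events.

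**Working it through.** The plan gives no figure to reproduce, so the check is day arithmetic.

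**Inputs.** SAP Table 3 gives the scheduled days: Day 1 = 1, Week 8 = 56, Week 20 = 140, Week 44 = 308, Week 48 = 336. The 28-day limit is from SAP 8.2.

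**Step 1: uncovered time for a participant followed to Week 48 without switching.** Window end = last dose day + 28. Uncovered = 336 − window end.

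| Last masked dose | Window ends | Uncovered days | Share of 336 |
|---|---|---|---|
| Day 1 | 1 + 28 = 29 | 336 − 29 = 307 | 91% |
| Week 8 (Day 56) | 56 + 28 = 84 | 336 − 84 = 252 | 75% |
| Week 20 (Day 140) | 140 + 28 = 168 | 336 − 168 = 168 | 50% |
| Week 44 (Day 308) | 308 + 28 = 336 | 0 | 0% |

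If the Week 44 dose is given 14 days early (Day 294) and no later dose follows, the window ends on Day 322, leaving 14 days to Day 336.

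**Step 2: when would an AE that ends treatment miss the discontinuation table?** Count the days in each dosing interval that lie more than 28 days after the preceding dose.
- Day 1 to Week 8: Days 30 to 55, 26 of 55 days.
- Week 8 to Week 20: Days 85 to 139, 55 of 84 days.
- Week 20 to Week 44: Days 169 to 307, 139 of 168 days.
- Total: 26 + 55 + 139 = 220 of 307 days (72%).

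This is calendar time, not the probability that an event is missed.

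**Step 3: would a longer window be enough?** Protocol 4.2.4 uses a safety follow-up of 8 weeks after the last dose. With 56 days in place of 28, the uncovered time is still 336 − 57 = 279, 336 − 112 = 224 and 336 − 196 = 140 days for a last dose on Day 1, Week 8 or Week 20. A longer window shrinks the gap but does not close it.

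**Step 4: when is nothing lost?** Under Protocol 7.1.1, "Treatment may be resumed after resolution of the adverse event and upon agreement with both the Investigator and medical monitor". If a later masked dose follows, the window extends to that dose + 28 days and the event is a TEAE. A participant who leaves the study has no further follow-up to count.

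**The case against.** A 28-day on-treatment window is defensible and matches the end-of-treatment visit in Protocol 7.1. It applies equally to both arms. The wording in Protocol 9.4.5 about adherence mainly defines who is analysed and sets no onset window. All of this stands.

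Four stronger readings are tempting, and the documents do not support them.
- **That late events are only listed.** The ATE and AESI tables are not limited to TEAEs. Under Protocol 8.3.6, AESIs include endophthalmitis, Grade 4 inflammation, a loss of 30 letters or more, and events needing surgery to save sight. SAP 6.1 counts reasons for stopping treatment by arm, and SAP 7.1.1.4 tabulates intercurrent events by arm, including discontinuation for study-eye AEs and for unrelated systemic AEs. These are categories, not MedDRA terms, and one of them combines study-eye AEs with lack of efficacy.
- **That the SAP does not intend to summarise all AEs.** The opening sentence of SAP 8.2 says it will. The gap is that no table in the list delivers this.
- **That participants who switch to open-label lose up to 20 weeks.** From the diagnosis visit they do not "nor receive further masked treatments". If the last dose means the last masked dose, the gap before a diagnosis visit at Week 8, 20, 32, 44 or 48 would be 4, 8, 8, 20 or 0 weeks (diagnosis week − last masked dose week − 4). But SAP 8.2 makes the start of open-label a separate cut-off, which would have almost nothing to do on that reading. If open-label doses count, the gap is 0. SoA-B attaches its footnote on study treatment to the open-label row, whereas SAP 8.1 leaves open-label doses out of the main exposure summary. This is a wording point, not a demonstrated loss.
- **That the 91%, 75% and 50% figures measure under-counted events, or that one arm is favoured.** They are follow-up time for an individual with a given last dose.

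**Conclusion.** The point holds for a defined group: participants who permanently stop masked treatment before Week 44, remain in follow-up, do not switch to open-label, and have an AE more than 28 days after the last dose that is neither an ATE nor an AESI. For them 168 to 307 days up to Day 336 lie outside the named TEAE, TESAE, inflammation and discontinuation tables. No all-AE or all-SAE table, and no table of non-ocular AEs leading to discontinuation, is named to fill the gap, although the endpoint is AE incidence up to Week 48.

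The figures assume dosing on SAP Table 3 days and follow-up to Week 48. The documents give neither the number of participants who stop nor any AE rates, so the number of missing events, and whether the arms differ, cannot be stated. The point should be fixed because a stated safety endpoint lacks a table that fully reports it. It does not affect the efficacy analyses.

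**What to change.** Keep the 28-day TEAE tables and amend SAP 8.2 as follows.
- Add incidence tables by treatment group, using the Safety Analysis Set grouping, for all AEs, all SAEs, intraocular inflammation, and AEs leading to study treatment discontinuation (ocular and non-ocular).
- Count onset from first dose through Week 48, or last study contact if earlier. Do not stop at the early termination visit when the participant stays in the study, since Protocol 7.2 asks for that visit when treatment alone is stopped.
- Cut these tables only at the start of open-label KSI-301. Flag, rather than drop, events after non-study anti-VEGF in the study eye.
- State whether the last dose date of study treatment includes open-label doses, so that no event before the switch falls between the TEAE tables and the post-switch table.

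The cost is a few more tables from data already collected. AE counts will be somewhat higher and will include events far from dosing that are less likely to be drug-related. Showing both sets of tables lets the reader see that distinction.
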